## 7.0 Outcome Measures

### 7.1 Primary Outcome

- 7.1.1 CREB phosphorylation determination by western blot in prostate tissue from men two hours after taking or not taking propranolol prior to prostate biopsy.

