## **2.0 Objectives**

### **2.1 Primary Objective**

- 2.1.1 To compare activation of ADRB2/PKA/BAD signaling pathway in the prostate glands of men two hours after taking or not taking propranolol prior to prostate biopsy or prostatectomy, as indicated by phosphorylated CREB.

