### **2.2 Secondary Objectives**

- 2.2.1 To compare activation of ADRB2/PKA/BAD signaling pathway in the prostate glands of men two hours after taking or not taking propranolol prior to prostate biopsy or prostatectomy as indicated by phosphorylated BAD.
- 2.2.2 To determine the difference in candidate transcript levels associated with ADRB2/PKA activation between individuals two hours after taking propranolol or not taking propranolol prior to prostate biopsy or prostatectomy.
- 2.2.3 To determine plasma propranolol levels in individuals taking propranolol two hours after administration prior to prostate biopsy or prostatectomy.
- 2.2.4 To determine if plasma catecholamine levels in men with prostate cancer can be used as a biomarker to identify patients who show activation of ADRB2 signaling pathway in prostate tumors.

- 2.2.5 To determine perceived stress level differences in men with prostate cancer prior to prostate biopsy or prostatectomy to examine possible association between perceived stress level and catecholamine levels in blood and activation of ADRB2 pathway in tumors
- 2.2.6 To determine perceived distress level differences in men with prostate cancer prior to prostate biopsy or prostatectomy to examine possible association between distress level and catecholamine levels in blood and activation of ADRB2 pathway in tumors.

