## **3.0 Study Population**

Patients recruited will be individuals scheduled for prostate biopsy or prostatectomy. For this study, 60 individuals will be recruited. Patients will be randomized to receive the treatment (or not) for a total of 30 patients receiving propranolol prior to biopsy or prostatectomy and 30 patients receiving no treatment. It is expected that approximately 10 (5 patients in each group) may have non-evaluable tumor tissue. In case the number of evaluable tumors will be less than 25 for each group, more patients will be recruited to accumulate 25 evaluable samples for each group.

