### 7.2 Secondary Outcomes

- 7.2.1 BAD phosphorylation by western blot in prostate tissue from men two hours after taking or not taking propranolol prior to prostate biopsy
- 7.2.2 Difference in levels of transcripts that reflect ADRB2/PKA activation as measured by real-time PCR in prostate tissue from men two hours after taking or not taking propranolol prior to prostate biopsy or prostatectomy.
- 7.2.3 Plasma propranolol levels as measured by fluorometric detection from men two hours after taking or not taking propranolol prior to prostate biopsy or prostatectomy.
- 7.2.4 Plasma catecholamine levels (including epinephrine) measured by ELISA from men two hours after taking or not taking propranolol prior to prostate biopsy or prostatectomy.
- 7.2.5 Self-perceived stress as measured by The Perceived Stress Questionnaire (Appendix C) from men on the day of surgery before taking propranolol, prior to prostate biopsy or prostatectomy.
- 7.2.6 Distress score as measured by The Distress Thermometer (Appendix D) from men on the day of surgery before taking propranolol, prior to prostate biopsy or prostatectomy.

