### 8.2 Primary Objective

Since this is a randomized trial, the two groups can be compared for CREB phosphorylation levels using a two-sample t-test. In addition to the 2-sample t-

test, descriptive statistics will be calculated for this primary outcome within each group. These statistics include n, mean, standard deviations and 95% confidence intervals.

Based on the preliminary data, the baseline level of CREB phosphorylation was 0.73 with a standard deviation of 0.26 . Using these values, we determined that there is 80% power to detect a difference of 0.21 between groups using a 2-sample t-test (alpha=0.05, 2-sided). Thus, if the control group has a value of 0.73 (based on the preliminary data) then we would be able to detect a difference if the value of CREB phosphorylation is below 0.52. Based on the preliminary data, this effect size is 0.81, and would correspond to a 29% relative change in CREB phosphorylation. This calculation is based on have 25 patients in each group being evaluable (i.e., having tumor tissue available to be evaluated). Sixty patients are to be enrolled to allow up to 10 patients (5 per group) to possibly not have evaluable tissue available at the time of analyses.

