### **8.5 Accrual Rate**

The accrual rate is anticipated to be 5 per month, thus recruitment should be complete within 12 months. Since analysis will occur on the samples that are taken during prostate biopsy, the overall length of this study is anticipated to be less than 18 months (allowing for the possibility that accrual goes slower than predicted or that time for lab analyses takes some time to be performed).

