### **14.2 Propranolol**

**Product description:** Propranolol hydrochloride is a stable, white, crystalline solid available in 10, 20, 40, 60 and 80 mg tablets. For this study, 40 mg tablets will be used.

**Solution preparation:** NA

**Storage requirements:** Store at room temperature. Protect from light

**Stability:** Propranolol is stable.

**Route of administration:** Take by mouth 2 hours before prostate biopsy

**Disposal:** Dispose of any unused tablets in line with local and institutional regulations.

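### The primary outcome names biopsy only while the trial enrols biopsy and prostatectomy patients, and the primary t-test has no procedure term

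*Combined protocol and SAP*

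**What the plan says.** Three places in the outcome and analysis sections refer to biopsy alone:

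- Section 7.1.1, primary outcome: "CREB phosphorylation determination by western blot in prostate tissue from men two hours after taking or not taking propranolol prior to prostate biopsy".
- Section 7.2.1, first secondary outcome: "BAD phosphorylation by western blot in prostate tissue from men two hours after taking or not taking propranolol prior to prostate biopsy".
- Section 8.5, on the study timeline: "analysis will occur on the samples that are taken during prostate biopsy".

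The administration line in section 14.2 also mentions only biopsy: "Take by mouth 2 hours before prostate biopsy".

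The rest of the protocol covers both procedures. Objective 2.1.1 compares men "two hours after taking or not taking propranolol prior to prostate biopsy or prostatectomy, as indicated by phosphorylated CREB", and objective 2.2.1 has the same scope for pBAD ("taking or not taking propranolol prior to prostate biopsy or prostatectomy as indicated by phosphorylated BAD"). Section 3.0 plans "a total of 30 patients receiving propranolol prior to biopsy or prostatectomy and 30 patients receiving no treatment". Section 4.2 describes separate tissue collection for each procedure, Appendix B labels both arms with either procedure, and outcomes 7.2.2 to 7.2.6 name both.

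For the analysis, section 8.2 says: "Since this is a randomized trial, the two groups can be compared for CREB phosphorylation levels using a two-sample t-test". It names no covariate or stratum. Sections 8.1 and 8.2 take a baseline mean of 0.73 and an SD of 0.26 from the group's earlier pilot study, which the reference list describes as a study of men undergoing prostate biopsies, and apply them to 25 evaluable patients per arm.

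**The concern.** There are three linked points.

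1. The primary outcome, the primary objective and the sample size do not name the same patients. Read literally, 7.1.1 excludes prostatectomy patients from the primary analysis, yet no section sets a minimum number of biopsy patients.

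2. If both tissues count, the t-test pools a biopsy sample (at least one core) with surgical specimens (at least three vials). Randomisation keeps the comparison unbiased. But if mean pCREB differs between the sources, that difference enters the error variance and costs power. Procedure is known before randomisation, so this loss can be avoided.

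3. The SD behind the 80% power comes from biopsies. No section says that it also holds for prostatectomy tissue.

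**Working it through.** **Inputs from the protocol.** Control mean 0.73, SD 0.26, difference 0.21, two-sided alpha 0.05, 25 evaluable per arm (section 8.1); plain two-sample t-test (section 8.2).

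**Inputs assumed, because the documents do not give them.** Prostatectomy share p, mean pCREB gap g between tissue sources, and the SD in prostatectomy tissue.

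**Step 1: the stated power.** Noncentrality = 0.21 / (0.26 × √(2/25)) = 2.86 on 48 degrees of freedom. Power is 79.9%, so the stated 80% reproduces. So do the effect size (0.21/0.26 = 0.81) and the relative change (0.21/0.73 = 29%).

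**Step 2: the literal, biopsy-only reading.** With the same difference and SD, 20, 15 or 10 evaluable biopsy patients per arm (assumed) give power of 70.2%, 57.0% or 40.1%.

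**Step 3: both tissues, no procedure term.** Overall SD = √(0.26² + p(1−p)g²). With p = 0.5 and gap 0.26, this is √(0.0676 + 0.25 × 0.0676) = √0.0845 = 0.291. The adjusted figures below come from simulating a linear model on arm and procedure (100,000 runs, simple randomisation).

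| Gap g | Overall SD | Unadjusted power | Difference detectable at 80%, unadjusted | Adjusted power (simulated) |
|---|---|---|---|---|
| 0 | 0.260 | 79.9% | 0.210 | 79.3% |
| 0.13 | 0.268 | 77.5% | 0.217 | 79.2% |
| 0.26 | 0.291 | 70.6% | 0.235 | 79.1% |
| 0.39 | 0.325 | 61.0% | 0.263 | 79.0% |

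Simulated unadjusted power agrees: 80.2%, 77.6%, 70.5% and 60.3%. Type I error is 4.9% to 5.1% for both analyses.

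**Step 4: break-even.** Unadjusted against adjusted power is 79.3% v 79.1% at gap 0.07 and 79.0% v 79.2% at gap 0.08. The term therefore pays for itself from a gap of about 0.08, which is 0.08/0.73 = 11% of baseline. Below that it costs at most about one point (80.2% v 79.3% at gap 0).

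**Step 5: other mixes.** At gap 0.26 with 10%, 20% or 30% prostatectomy, unadjusted power is 76.4%, 73.7% or 71.8%; adjusted power is about 79% in each case.

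**Step 6: arms balanced within procedure.** Section 4.2 describes randomisation into two groups separately under each procedure heading, which can be read as randomisation within procedure. If the arms are balanced that way, unadjusted power at the four gaps is 79.8%, 77.9%, 72.2% and 62.8%, and unadjusted type I error is 5.0%, 4.4%, 2.9% and 1.6%. The adjusted model keeps about 80% power and 5% error.

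**Step 7: a different prostatectomy SD.** With no gap, a 50:50 mix and a prostatectomy SD of 0.20, 0.30 or 0.40, power is 87.9%, 73.4% or 57.9% unadjusted and 87.2%, 72.5% or 57.0% adjusted. The procedure term does not protect against this.

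**The case against.** The strongest reply is that this is a wording slip plus an optional covariate. The neighbouring outcomes name both procedures, section 8.2 counts all sixty patients, and section 4.2 uses biopsy as loose shorthand in a sentence that goes on to mention surgery. Section 8.5 is a timeline paragraph and 14.2 an administration line; neither defines an analysis population. An unadjusted t-test is an acceptable primary analysis for a small randomised pilot. The larger assumed gaps are demanding: 0.26 is 36% of baseline and exceeds the 0.21 effect the trial is powered for. A 50:50 mix gives the greatest loss for a given gap. With 10% to 20% prostatectomy and a gap of 0.13, unadjusted power is 79.0% to 78.3%, close to the adjusted figure. The same assay and the same ratio to total protein are used for both tissues, and the laboratory plan will test laser capture of epithelial cells, which could narrow differences in tissue composition. Stratified randomisation is not stated anywhere. The 80% is not an arithmetic error, and a smaller prostatectomy SD would raise it.

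Most of this stands. The gap is unknown and may be small, the test is not biased, and the results for arms balanced within procedure depend on one reading of section 4.2. But the current text of the primary outcome still excludes patients whom the objective includes. The trade-off also favours the term: at most about one point of power lost, against about nine points gained at a gap of 0.26 in a 50:50 mix. The SD point would not justify a change by itself; it only calls for a stated assumption.

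**Conclusion.** The concern holds. The inconsistency in the primary outcome is certain from the text and should be corrected, although it is probably a drafting omission. The missing procedure term is a conditional loss of precision, not a bias. With 25 per arm, a within-procedure SD of 0.26, a true difference of 0.21 and a 50:50 mix, unadjusted power falls from 79.9% to 77.5%, 70.6% or 61.0% at gaps of 0.13, 0.26 or 0.39, while the adjusted model stays at about 79%. The documents support no particular gap or mix, so these figures show sensitivity and are not forecasts. The 80% is correct on its own inputs; whether a biopsy SD holds for prostatectomy tissue cannot be judged from the documents.

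**What to change.** - **Outcome wording.** Amend 7.1.1, 7.2.1 and 8.5 to name both procedures, in line with objectives 2.1.1 and 2.2.1. If biopsy tissue alone is really meant, say so and plan for 25 evaluable biopsy patients per arm. The wording in 14.2 must be reconciled with section 4.2.
- **Primary analysis.** In 8.2, specify a linear model of the pCREB/total CREB ratio on arm and procedure, reporting the adjusted difference with its 95% confidence interval. In 8.3, use the same model for pBAD and the transcripts.
- **Timing.** Fix this before any CREB data by arm are reviewed, including at the interim in 8.4, because treatment is open and that review looks at CREB phosphorylation in treated patients. If such data have already been seen, keep the t-test as primary and report the model as a sensitivity analysis.
- **SD.** In 8.1, state that the 80% assumes a within-procedure SD of 0.26, taken from biopsies, for both tissue sources. In 8.2, report the SD by procedure.
- **Data.** Record procedure as an analysis variable. The eligibility checklist has one combined row and the randomisation form prints both procedures for each arm. No visible form has a separate field, though the worksheet tables in Appendices J to M could not be read.

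The cost is wording in seven sections, one recorded variable and one degree of freedom (about one point of power if there is no gap). Stratified randomisation by procedure is optional.

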### 7.2 Secondary Outcomes

- 7.2.1 BAD phosphorylation by western blot in prostate tissue from men two hours after taking or not taking propranolol prior to prostate biopsy
- 7.2.2 Difference in levels of transcripts that reflect ADRB2/PKA activation as measured by real-time PCR in prostate tissue from men two hours after taking or not taking propranolol prior to prostate biopsy or prostatectomy.
- 7.2.3 Plasma propranolol levels as measured by fluorometric detection from men two hours after taking or not taking propranolol prior to prostate biopsy or prostatectomy.
- 7.2.4 Plasma catecholamine levels (including epinephrine) measured by ELISA from men two hours after taking or not taking propranolol prior to prostate biopsy or prostatectomy.
- 7.2.5 Self-perceived stress as measured by The Perceived Stress Questionnaire (Appendix C) from men on the day of surgery before taking propranolol, prior to prostate biopsy or prostatectomy.
- 7.2.6 Distress score as measured by The Distress Thermometer (Appendix D) from men on the day of surgery before taking propranolol, prior to prostate biopsy or prostatectomy.

## 8.0 Analytic Plan

### 8.1 Power Calculation/Sample size

Based on the preliminary data, the baseline level of CREB phosphorylation was 0.73 with a standard deviation of 0.26 . Using these values, we determined that there is 80% power to detect a difference of 0.21 between groups using a 2-sample t-test (alpha=0.05, 2-sided). Thus, if the control group has a value of 0.73 (based on the preliminary data) then we would be able to detect a difference if the value of CREB phosphorylation is below 0.52. Based on the preliminary data, this effect size is 0.81, and would correspond to a 29% relative change in CREB phosphorylation. This calculation is based on have 25 patients in each group being evaluable (i.e., having tumor tissue available to be evaluated).

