#### **4.2 Methods**

#### **Compare activation of ADRB2/PKA/BAD signaling pathway in the prostate glands of men who take or do not take ADRB2-selective beta blockers**

##### **Patients scheduled for prostate biopsy.**

The research staff screens the OR and clinic schedules for potential patients and provides a list to the investigator. [name] or co-Investigator will discuss the study with the patient and inform the research nurse or coordinator (research staff) about the patients who agreed to participate in the study. Research staff will inform Tissue Procurement Lab (Director [name]; [name], Tumor Procurement Coordinator) and courier about the scheduled date and time when prostate samples will be collected.

On the day of sample collection [name] lab will prepare box with dry ice for prostate biopsy samples, a box with wet ice for blood samples as well as 2 ml cryovials (Corning, cat#430488) to collect biopsies and tubes to collect blood (Na heparin, green-capped tube, 10 ml total blood volume).

Courier will pick up boxes from Tissue Procurement Lab (Director [name]; [name], [contact]) and deliver to research staff at Charlois clinic ([name]).

Recruited patients scheduled for prostate biopsy will be randomized into two groups. Group one will receive 40 mg propranolol given by research nurse 2 hours prior to prostate biopsy. The research nurse should withhold drug and contact treating physician if SBP <120 or HR < 63. Group two will receive no treatment.

All patients will fill out stress surveys on the biopsy day.

All patients will give approximately 10 mL of blood approximately 20 min prior to prostate biopsy to test plasma catecholamine levels (collected in 10 mL green top tube (sodium heparin) and sent on ice within 1 hour to clinical lab for processing) and propranolol level (collected in 10 mL green top tube (sodium heparin) and sent on ice to The Tissue Procurement lab for processing and storage as described below). For group one that takes propranolol, this blood sample will be drawn at 1.5 -2 hours after taking the propranolol tablet.

For the biopsy, at least 1 core of the prostate specimen is to be flash frozen (on dry ice -80C) for laboratory analysis. Each biopsy sample will be collected into separate cryovials. The samples will be picked up by courier at Charlois clinic and delivered to Tissue Procurement laboratory.. The tissue samples will be frozen at -80 C.

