### **8.4 Interim Analysis**

An interim analysis will occur after 10 patients (5 in each group) are recruited to determine if dosing or administration route of propranolol needs to be adjusted. This interim analysis will not include any statistical testing, but rather will be used to assess the safety of the trial.

If CREB phosphorylation will be observed in patients with epinephrine blood levels over 1nM who took propranolol, the dose of propranolol will be increased to 80mg. Exclusion criteria for this dose will be reviewed based on interim analysis.

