### **Safety Review**

Safety will be addressed on a per patient basis as described in Section 5.0 and as reiterated below. Because this pilot study involves only 1 dose of medication (initially 40mg; if 40mg is not effective in inhibiting CREB phosphorylation dose will be increased to 80mg) with a peak effect expected in 1-4 hours and a half-life of 3-6 hours, the safety assessment window will be in the perioperative period for up to 4 hours after dosing. Blood pressure will be monitored at 3h and 4h after the propranolol is taken. Patients will be allowed to leave if SBP >90. If blood pressure not acceptable after 4 hours, the patient will continue to be monitored and may receive IV fluids if SBP/DBP <90/60 after 6h post dose.

If there is CTCAE grade 3 bradycardia or hypotension, then the dose for subsequent patients will be modified per section 5.2. The study will be terminated if grade 4 or 5 cardiac events attributable to propranolol dosing occur. While safety will be addressed promptly on a per patient basis, a review of all AEs will occur at the safety interim analysis after 10 patients have been accrued (5 in each group). If other safety events are identified by the investigators at this interval analysis, then the propranolol dosing may be modified for subsequent subjects as directed by Section 5.2 or in a manner designated by the PI to ensure safety of the patients.

Finally, if a safety event as described in Section 5.1.1 occurs, the study will be locked and all activities suspended for 24 hours to further evaluate patient recovery and to monitor for other potential events. If patient recovery is deemed acceptable by the PI, the trial will be unlocked with subsequent patients following the modified dose reduction plan as described in Section 5.2.

Occurrence of an SAE other than those listed above will be addressed following the SAE protocol (Appendix F).

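### The 80% power in 8.1 holds only if the dose stays the same; after the dose increase planned in 8.4, pooling as randomised leaves about 59–73%

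*Combined protocol and SAP*

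**What the plan says.** All references are to the combined protocol and SAP.

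- **Power (8.1, repeated in 8.2).** With a control mean of 0.73 and SD 0.26, "we determined that there is 80% power to detect a difference of 0.21 between groups using a 2-sample t-test (alpha=0.05, 2-sided". The basis is 25 evaluable men per group. The section adds that "we would be able to detect a difference if the value of CREB phosphorylation is below 0.52".
- **Planned dose change (8.4).** "An interim analysis will occur after 10 patients (5 in each group) are recruited". If CREB phosphorylation is seen in propranolol-treated men whose epinephrine exceeds 1 nM, "the dose of propranolol will be increased to 80mg". The Safety Review words the condition differently: "if 40mg is not effective in inhibiting CREB phosphorylation dose will be increased to 80mg".
- **Primary analysis (8.2).** "the two groups can be compared for CREB phosphorylation levels using a two-sample t-test". There is no dose term, no exclusion by dose and no named analysis set.
- **Top-up (3.0).** "In case the number of evaluable tumors will be less than 25 for each group, more patients will be recruited". Evaluable samples are counted per group, whatever the dose.
- **Withheld drug (4.2, biopsy patients; a similar rule applies to prostatectomy).** "The research nurse should withhold drug and contact treating physician if SBP <120 or HR < 63". No section says how such a man is analysed.
- **Expected result (4.2, laboratory plan, item 3).** If propranolol works, CREB phosphorylation is not expected to be seen in treated men. The same item measures it as a ratio of phosphorylated to total CREB.

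**The concern.** The power statement concerns the difference between two group means, so it holds when the shift averaged over all evaluable propranolol men is 0.21. The dose increase in 8.4 is a written path, not a deviation. It is taken when the first dose is judged not to be working, so on that path the men already treated are expected to show less than the final-dose shift. As 8.2 and 3.0 are written, those men still count towards the 25 and still enter the t-test. The group mean shift is diluted, and a final dose that truly delivers 0.21 is missed more often than the stated 20% of the time.

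A second problem is that the trigger and the sample size are on different footings. Item 3 of 4.2 and section 8.4 treat phosphorylation as seen or not seen. Section 8.1 treats it as a continuous ratio, and the drug succeeds if the treated mean falls to 0.52. The decision to change the dose, and with it the dilution, depends on a threshold that is not stated on that ratio.

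**Working it through.** **Inputs.** Control mean 0.73, SD 0.26, difference 0.21, two-sided alpha 0.05, 25 evaluable per group (8.1); 5 treated men at the interim (8.4); 25 of 30 per group expected evaluable (3.0); accrual 5 per month (3.4, 8.5).

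**1. The plan's own figure.** The noncentrality is 0.21 / (0.26 × √(2/25)) = 0.21 / 0.0735 = 2.86 on 48 degrees of freedom. Power is 79.9% and the difference detectable at 80% is 0.210. Also 0.21/0.26 = 0.81 and 0.21/0.73 = 29%. Section 8.1 is correct on its inputs.

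**2. Early-dose men in the test.** Expected evaluable: 5 × 25/30 = 4.2, so k = 4 or 5.

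**3. Dilution if the early dose has no effect and the final dose shifts by d = 0.21.**
- Mean shift = d × (25 − k)/25, which is 0.21 × 21/25 = 0.176 for k = 4 and 0.21 × 20/25 = 0.168 for k = 5.
- Mixing two doses adds variance f(1 − f)d² to the treated arm, with f = (25 − k)/25. For k = 4 this is 0.84 × 0.16 × 0.0441 = 0.0059, and for k = 5 it is 0.80 × 0.20 × 0.0441 = 0.0071, each added to 0.26² = 0.0676.

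| Early men (k) | Power for 0.21, noncentral t | Simulation (200,000 trials) | Final-dose shift for 80% power |
|---|---|---|---|
| 0 | 79.9% | – | 0.210 |
| 4 | 63.3% | 63.6% | 0.258 |
| 5 | 58.8% | 58.9% | 0.274 |

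With the SD simply held at 0.26, power is 65.2% and 61.0%, and the required shifts are 0.250 and 0.263. A rounded statement is 59–64% power and a required shift of about 0.26–0.27. The final-dose value must then be about 0.73 − 0.26 = 0.47 to 0.73 − 0.27 = 0.46, not 0.52.

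**4. Early dose with half the effect (0.105).** Mean shift is 0.21 × (25 − k/2)/25 = 0.193 (k = 4) or 0.189 (k = 5). Power is 73.1% or 71.2% with SD 0.26; simulation with the mixed doses gives 72.4% or 70.8%. The required final-dose shift is 0.2103 × 25/23 = 0.229 or 0.2103 × 25/22.5 = 0.234.

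**5. Variations.**
- No enrolment pause during the assay is stated. Each month would add about 2.5 × 25/30 = 2.1 evaluable early-dose men. With no early effect, k = 6 gives 54% and k = 8 gives 45%. The length of any delay is an assumption.
- Early treated men dropped and not replaced (20–21 against 25): 75–76%.
- Only men randomised to both arms after the change, 20 per arm: 70%.
- All 30 per group evaluable, k = 5, no early effect: 71%.

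**6. Trigger against sample size.** A treated mean of 0.52 is 0.52/0.73 = 71% of control. A drug achieving exactly the powered effect therefore leaves measurable phosphorylation in the average treated man. Read literally, the condition in 8.4 can be met in a high-epinephrine man even though the drug is doing what 8.1 was sized to detect.

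**The case against.** Section 8.1 states a between-group difference, which already means a group average, and its arithmetic is right. A reader might infer that the sample size is miscalculated; it is not.

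A reader might also take 59–64% as the power of this trial. That range needs a dose increase and no effect at all in every early man. Neither 8.4 nor the Safety Review says this: a first dose judged ineffective may still have a partial effect, and the trigger might be met by a single man with epinephrine above 1 nM. With half the effect the loss is about 7–9 points. Moreover, 25 is a floor and not a cap, so more evaluable men would help.

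That the early men stay in the test is inferred from the silence of 8.2 and 3.0. The inference is sound, because 8.2 rests the comparison on randomisation and 8.1 defines evaluable by tissue alone. It should still be written down, since dropping or restricting gives a different estimate and a different power.

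Two further readings are tempting but unsupported. One is a figure for how often the trigger would fire on an effective drug: the documents give no CREB distribution for men with epinephrine above 1 nM. The other is a power loss from withheld doses: the documents give no count, and 3.2 already excludes men below the same blood pressure and heart rate limits at baseline.

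Finally, the Safety Review calls this a pilot study. It nevertheless makes a formal 80% claim for a two-sided 0.05 test.

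**Conclusion.** The point stands in conditional form. The stated 80% is right if the dose is unchanged. If the dose is raised under 8.4 and the groups are pooled as randomised, power for a final-dose shift of 0.21 is about 59–64% with no early effect and about 71–73% with half the effect. In the no-effect case, a final dose that gives 0.21 is missed in about 36–41% of trials instead of 20%.

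These figures assume 25 evaluable men per group, SD 0.26, 4–5 evaluable early-dose men, a dose change straight after the tenth patient, and retention of the early men. Continued enrolment during the assay would lower them.

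The mismatch between the trigger and the sample size stands as a contradiction between 4.2 item 3, 8.1, 8.4 and the Safety Review. Its frequency cannot be calculated from the documents. If the dose never changes, the power figure in 8.1 needs no revision.

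**What to change.** 1. In 8.1 and 8.2, state that 80% applies without a dose change. Give the range of about 59–73% for the as-randomised pooled analysis after one, with the early-effect assumption behind each end.
2. In 8.2, before the interim, define the primary analysis as all randomised men with evaluable tissue, in their assigned group, including men whose drug was withheld. Prespecify a sensitivity analysis of men randomised to both arms after the change, and state its power (about 70% with 20 per arm).
3. Reconcile 4.2 item 3, 8.1, 8.4 and the Safety Review so that the condition for a dose change has one wording, on the same ratio scale as 0.73 and 0.52. No dose or cut-off is proposed here.

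The cost is wording, one extra analysis and a less favourable stated power if the dose changes. No additional patients are required. If the sponsor wanted 80% in the post-change comparison alone, topping up from 20 to 25 per arm would need 10 more evaluable men, or 10 × 30/25 = 12 recruited, which is 12/5 = 2.4 months at the planned accrual.
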